Appendix 1: Numerical Pain Scale NRS for Joint Pain

INSTRUCTIONS

1. Place an "X" in the box below that indicates the amount of pain the subject feels in index / contralateral shoulder joints in the last 24 hours.

0	1	2	3	4	5	6	7	8	9	10
No Pain		Mild		Moderate			Severe		Worst Pain	

Appendix 2 Disabilities of the Arm, Shoulder and Hand DASH

DISABILITIES OF THE ARM, SHOULDER AND HAND

Please rate your ability to do the following activities in the last week by circling the number below the appropriate response.

		NO DIFFICULTY	MILD DIFFICULTY	MODERATE DIFFICULTY	SEVERE DIFFICULTY	UNABLE
1,	Open a tight or new jar.	1	2	3	4	5
2.	Write.	1	2	3	4	5
3.	Turn a key.	1	2	3	4	5
4.	Prepare a meal.	.1	2	3	4	5
5.	Push open a heavy door.	1	2	3	4	5
6.	Place an object on a shelf above your head.	1	2	3	4	5
7.	Do heavy household chores (e.g., wash walls, wash floors),	1	2	3	4	5
8.	Garden or do yard work.	1	2	3	4	5
9.	Make a bed.	1	2	3	4	5
0.	Carry a shopping bag or briefcase.	1 -	2	3	4	5
1.	Carry a heavy object (over 10 lbs).	1	2	3	4	5
2.	Change a lightbulb overhead.	1	2	3	4	5
3.	Wash or blow dry your hair.	1	2	3	4	5
4.	Wash your back.	1	2	3	4	5
5.	Put on a pullover sweater.	1	2	3	4	5
6.	Use a knife to cut food.	1	2	3	4	5
7.	Recreational activities which require little effort (e.g., cardplaying, knitting, etc.).	1	2	3	4	5
B.	Recreational activities in which you take some force or impact through your arm, shoulder or hand (e.g., golf, hammering, tennis, etc.).	1	2	3	4	5
9.	Recreational activities in which you move your arm freely (e.g., playing frisbee, badminton, etc.).	1	2	3	4	5
0.	Manage transportation needs (getting from one place to another).	1	2	3	4	5
1.	Sexual activities.	1	2	3	4	5

Version 2.0 14 Aug 2019 Confidential Page 36 of 38

DISABILITIES OF THE ARM, SHOULDER AND HAND

		NOT AT ALL	SLIGHTLY	MODERATELY	QUITE A BIT	EXTREMELY
22.	During the past week, to what extent has your arm, shoulder or hand problem interfered with your normal social activities with family, friends, neighbours or groups? (circle number)	1	2	.3	4	5
		NOT LIMITED AT ALL	SLIGHTLY LIMITED	MODERATELY LIMITED	VERY LIMITED	UNABLE
23.	During the past week, were you limited in your work or other regular daily activities as a result of your arm, shoulder or hand problem? (circle number)	1	2	3	4	5
Ple	ise rate the severity of the following symptoms in the last we	ek. (orde num	(ber)			
		HONE	MILD	MODERATE	SEVERE	EXTREM E
24.	Arm, shoulder or hand pain,	1	2	3	4	5
25.	Arm, shoulder or hand pain when you performed any specific activity.	1	2	3	4	5
26.	Fingling (pins and needles) in your arm, shoulder or hand.	1	2	3	4	5
27.	Weakness in your arm, shoulder or hand.	1	2	- 3	4	5
28.	Stiffness in your arm, shoulder or hand.	1	2	3	4	5
	0	NO DIFFICULTY	MILD DIFFICULTY	MODERATE DIFFICULTY	SEVERE DIFFICULTY	SO MUCH DIFFICULTY THAT I CAN'T SLEEP
29.	During the past week, how much difficulty have you had sleeping because of the pain in your arm, shoulder or hand (circle number)	? 1	2	3	4	5
	9	STRONGLY DISAGREE	DISAGREE	NEITHER AGREE NOR DISAGREE	AGREE	STRONGLY AGREE
0.	I (eel less capable, less confident or less useful because of my arm, shoulder or hand problem, (circle number)	1	2	3	4	5

A DASH score may not be calculated if there are greater than 3 missing items.

Appendix 3 Patient Global Assessment

To be assessed by the Subject as the first questionnaire.

The pain the subject felt in INDEX joint caused by osteoarthritis during the last 24 hours.

Have the Subject record their response with an "X":

Think about the pain you felt in your STUDY shoulder caused by your osteoarthritis during the last 24 hours.

"Considering all the ways the osteoarthritis in your STUDY shoulder affects you, what is your assessment of how much your STUDY shoulder is bothering you today?"

0	1	2	3	4	5	6	7	8	9	10
No Pain		Mild		Moderate			Severe		Worst Pain	

Appendix 4 Change History

Location of Change	Original Text	Changed Text	Reason
Inclusion Criteria	2. Body Mass Index (BMI) ≤ 45 kg/m²	2. Body Mass Index (BMI) ≤ 35 kg/m²	Alignment of BMI with value stated in screening section
6.6.3 Baseline Inclusion Criteria	1. NRS pain ≥4 and ≤8	1. NRS pain ≥4 and ≤9	Alignment of NRS score with value stated in screening section
6.62 Screening Exclusion Criteria	3. NRS pain ≥ 3 the contralateral joint	3. NRS pain ≥ 3 in the contralateral joint	Clarification of criteria

#### 1.0 Introduction

This document presents the statistical analysis plan (SAP) for the Anika Therapeutics, Inc. protocols MON 18-01 (Hip), MON 18-02 (Shoulder), and MON 18-03 (Ankle). This SAP incorporates the data listings, summary tables, and statistical analyses. This document is based on the original final protocols and case report forms (CRFs) for each study.

The three studies are the same except for the anatomical area of interest and so all of the analyses will be consolidated into a single SAP.

#### 2.0 Study Design

This is a prospective, post market clinical follow-up (PMCF) multi-center, open-label study to evaluate the residual risk of injections of MONOVISC for relief of pain in patients with a diagnosis of an osteoarthritic hip joint (MON 18-01), shoulder joint (MON 18-02), and ankle joint (MON 18-03).

The subjects in each of these study will be patients with a diagnosis of osteoarthritic (OA) joint who the investigator determines are appropriate candidates for treatment with a viscoelastic injection of MONOVISC.

In each study, up to 25 subjects will be enrolled at up to 20 investigational sites in the EU. Subject participation will last approximately 6 Months, with visits scheduled at Screening, Baseline, 1 month, 3 month and 6 months.

#### 3.0 Objectives

The goal of these studies is to demonstrate the clinical improvement and safety in patients treated with MONOVISC for hip osteoarthritis, shoulder osteoarthritis, and ankle osteoarthritis. Specifically, this study will provide confirmation to the effectiveness and safety of MONOVISC at relieving the specified joint pain to 6 months post-treatment.

#### PRIMARY ENDPOINT:

• Reduction of index joint Numerical Rating Scale (NRS) pain on walking from baseline to 6 Months post injection (MON 18-01), joint pain from baseline to 6 Months post injection (MON 18-02), and pain on walking from baseline to 6 Months post injection (MON 18-01).

#### **SECONDARY ENDPOINTS:**

- Improvement in Lequesne Hip index joint from baseline to 6 months post injection. (MON 18-01 only)
- Improvement in DASH score for index joint from baseline to 6 months post injection (MON 18-02 only)

- Improvement in AOFAS index joint from baseline to 6 months post injection (MON 18-03 only).
- Improvement in Patient Global Assessment (PGA) from baseline to 6 months post injection.
- OMERACT-OARSI responder rate in the index joint at 6 months post injection.
- Time to treatment failure
- Reduction in Medication usage from baseline to 6 months post injection.

#### **EXPLORATORY ENDPOINTS**

Any comparisons across timepoints (baseline to 6 months) not described in the primary or secondary endpoints, including but not limited to:

- Demographics
- Medical History
- History of joint osteoarthritis
- Rescue Medication Use
- Treatment Failure
- Injection procedure
- Concomitant medications
- Non-drug therapy

#### SAFETY ENDPOINT:

The incidence, severity, and relationship to treatment of all Adverse Events (AE) will be collected from the treatment injection to the 6 month assessment.

#### 4.0 Statistical Methods in Protocol

#### 4.1 STATISTICAL METHODS

This Statistical Analysis Plan provides the details of the statistical analysis of the study data that is described in the protocol.

#### 4.1.1Sample Size

The primary analysis will be the mean change in index joint pain from baseline to 6 months as measured by the Numerical Rating Scale.

The hypothesis to be tested is:

```
H_0: \mu_{DMON} = 0 versus H_A: \mu_{DMON} > 0.
```

In this hypothesis,  $\mu_{DMON}$  is the mean change in pain on walking from baseline at 6 Months in MONOVISC treated patients.

The data will be analyzed via a one sample t-test.

It is assumed that a mean change in pain from baseline of 2 points represents a clinically significant improvement with a standard deviation of 2 - 2.5 points, for 80% power and alpha of 5% then a total of 15 subjects are required. To ensure sufficient subjects are available at the 6 month follow up, it is proposed to enroll and treat at least 25 subjects which should be more than adequate to demonstrate that treatment of the study population with MONOVISC would reduce joint pain at 6 months.

Single sites should not enroll more than 50% of the total enrollment.

#### 4.1.2 Primary Efficacy Endpoint

# 4.1.2.1 The mean change in index joint Pain from baseline to 6 Months as measured with NRS comparing the Monovisc treated group to baseline measurements.

The primary analysis will be the mean change in index joint pain from baseline to 6 months as measured by the Numerical Rating Scale.

The hypothesis to be tested is:

```
H_0: \mu_{DMON} = 0 versus H_A: \mu_{DMON} > 0.
```

In this hypothesis,  $\mu_{DMON}$  is the mean change in pain from baseline at 6 Months in MONOVISC treated patients.

The data will be analyzed via a one sample t-test.

This will be analyzed using SAS PROC UNIVARIATE. ODS statements will be used to output the descriptive statistics and p-values into data sets that can be easily displayed using PROC REPORT.

The tables for this analysis will be displayed as follows showing all time points for reference:

This analysis will be performed for each of the protocols

Summary of Differences in Mean Responses over time -

| Time Perios |                       |                 | Visit Result |                      |
|-------------|-----------------------|-----------------|--------------|----------------------|
|             | Descriptive Statistic | Baseline Result |              | Change from Baseline |
| 1 Week      | N                     |                 |              |                      |
|             | Mean                  |                 |              |                      |
|             | Std.Drv               |                 |              |                      |
|             | Median                |                 |              |                      |
|             | (Min,Max)             |                 |              |                      |
|             | p-value diff=0        |                 |              |                      |
| 1 Month     | N                     |                 |              |                      |
|             | Mean                  |                 |              |                      |
|             | Std.Drv               |                 |              |                      |
|             | Median                |                 |              |                      |
|             | (Min,Max)             |                 |              |                      |
|             | p-value diff=0        |                 |              |                      |
| • • •       |                       |                 |              |                      |
| 6 Months    | N                     |                 |              |                      |
|             | Mean                  |                 |              |                      |
|             | Std.Drv               |                 |              |                      |
|             | Median                |                 |              |                      |
|             | (Min,Max)             |                 |              |                      |
|             | p-value diff=0        |                 |              |                      |

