6.6 Enrollment Criteria

At screening visit:

- 6.6.1 Screening Inclusion Criteria
 - 1. Age 18 years or older
 - 2. Body Mass Index (BMI) $\leq 35 \text{ kg/m}^2$
 - 3. Diagnosis of symptomatic osteoarthritic joint in the index joint (Kellgren-Lawrence grade I to III or Guyette grade I to III) to be treated with MONOVISC injection.
 - 4. Failed conservative treatment for joint osteoarthritis.
 - 5. NRS pain ≥4 and ≤9 in the index joint.
 - 6. Subject must be willing to abstain from other treatments of the index joint for the duration of the study.
 - 7. Subject is willing to discontinue all analgesics including NSAIDs, except acetaminophen/paracetamol, at least seven days before the treatment injection and through the completion of the study.
 - 8. Subject is willing to use only acetaminophen/paracetamol (up to a maximum of 4.0 grams per day per the package insert) for the treatment of joint pain for the duration of the study. At least forty-eight hours prior to the Baseline Visit and each follow-up assessment, the subject is willing to discontinue use of acetaminophen/paracetamol.
 - 9. Subject is willing to maintain a stable dose of oral glucosamine and/or chondroitin sulfate products throughout the study, if taken prior to signing the informed consent form (ICF).
 - 10. Able and willing to provide signed informed consent.

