7.5 Follow-Up Visits

All study subjects will have follow-up visits at 1, 3 and 6 Months after Baseline to evaluate the joint pain score and to assess adverse events.

The subject should be contacted at least 48 hours prior to their scheduled assessments to be reminded of the required assessment (and applicable wash out period) and to schedule the date and time of contact. At least three documented attempts will be made to contact the subject in order to accomplish maximum subject compliance with the follow-up schedule.

The following tests will be performed at the follow-up visits at 1, 3, and 6 months.

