9.2.3 Subject Populations

The Safety Population will be defined as all subjects who undergo Study Treatment, and the safety analysis will be performed on this population.

The primary analysis on the primary endpoint will be performed on the Intent to Treat (ITT) population, defined as all patients who were treated in the study. All Primary and Secondary endpoints will be analyzed using the ITT population.

A secondary analysis will be conducted on the Per Protocol (PP) population. Since the primary

endpoint is at 6 Months, this is all subjects who complete the 6 Month assessment and who do not have a major deviation from the protocol. For all other assessments, this is defined as the subjects who complete those assessments according to the protocol.

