13.4 Protocol Deviations

Deviations from the protocol include, but are not limited to missed assessments, out of window assessments, etc. All protocol deviations will be documented and explained. All subjects with protocol deviations will continue to be followed for improvement and safety. Analysis of study data will be done on both the ITT and PP populations.

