#### 4.5 SUBJECT POPULATIONS

All safety analyses will be conducted on all subjects who undergo treatment in any group.

The Safety Population will be defined as all subjects who undergo at least one Study Treatment, and the safety analysis will be performed on this population.

The primary analysis on the primary endpoint will be performed on the Intent to Treat (ITT) population, defined as all patients who were enrolled in the study. All Primary and Secondary endpoints will be analyzed using the ITT population.

A secondary analysis will be conducted on the Per Protocol (PP) population. Since the primary endpoint is at 6 Months, this is all subjects who complete the 6 Month visit and who do not have a major deviation from the protocol. For all other assessments, this is defined as the subjects who complete those assessments according to the protocol.

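### The primary 6-month pain result has no missing-data rule: subjects without a 6-month score drop out of the ITT mean, and no planned analysis addresses bias if loss is related to response

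*SAP*

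**What the plan says.** SAP 4.1.2.1 defines the primary analysis as the mean change in index-joint NRS pain from baseline to 6 months: "The data will be analyzed via a one sample t-test", run in PROC UNIVARIATE. Protocol 9.1 names the same test. The results table lists N, mean, SD, median, range and p-value by visit, with visits other than month 6 shown for reference. It has no confidence-interval row.

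The analysis is assigned to the ITT set, which is defined in two ways. SAP 4.5 has "population, defined as all patients who were enrolled in the study"; protocol 9.2.3 has "population, defined as all patients who were treated in the study". The one secondary set is per protocol (PP), and at 6 months "this is all subjects who complete the 6 Month visit and who do not have a major deviation from the protocol". At other visits PP consists of those who completed that visit according to the protocol.

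Loss is handled in three places. SAP 4.1.1 and protocol 9.1 enrol 25 against 15 required, so that enough subjects remain at 6 months. Protocol 7.5 asks for persistence: "At least three documented attempts will be made to contact the subject in order to accomplish maximum subject compliance with the follow-up schedule". Protocol 13.12 records the reason for withdrawal and seeks the return of withdrawn subjects for safety evaluations; it does not mention pain scores. SAP 4.6 allows unspecified further analyses if certain factors are thought to influence the endpoints. Neither document contains an imputation rule, a missing-data assumption, a repeated-measures model or a missing-data sensitivity analysis.

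**The concern.** A one-sample t-test on a change score can use only subjects who have that score. Without an imputation rule, the ITT result at 6 months is a completer result. The PP result at 6 months is drawn from the same completers, so agreement between the two would say nothing about the subjects who left.

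The trial has no control arm, so the 6-month mean change is its main efficacy result. If subjects with little benefit leave, that mean is too high. If subjects who feel well stop attending, it is too low. Month 1 and 3 scores could show which is happening and largely correct it, but they do not enter the 6-month estimate.

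**Working it through.** **Inputs from the plan.** 25 enrolled; 15 required; mean change 2 points; SD 2 to 2.5; 80% power; alpha 5%; NRS at months 1, 3 and 6. Positive change means improvement.

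**Assumed inputs.** Loss rate and pattern, true mean and between-visit correlation. The plan gives none of these apart from the 2-point target.

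**Step 1: the plan's own figure.** Two-sided 5%, SD 2.5, normal approximation: ((1.960 + 0.842) × 2.5 / 2)² = 12.3, so 13. The exact noncentral-t calculation gives 15 (power 0.821), which matches the plan. With all 25 observed, power is 0.970. Going from 25 to 15 allows 1 − 15/25 = 40% loss. This allowance concerns power only.

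**Step 2: bias of the completer mean.** Completer mean − all-treated mean = loss fraction × (completer mean − mean of the missing). For a gap of 2 points in either direction:

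| Observed | Loss | Bias |
|---|---|---|
| 22 of 25 | 12% | 0.12 × 2 = ±0.24 |
| 20 of 25 | 20% | 0.20 × 2 = ±0.40 |
| 15 of 25 | 40% | 0.40 × 2 = ±0.80 |

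**Step 3: simulation.** n = 25, SD 2.5, true mean changes 2.0, 1.8 and 1.5 at months 1, 3 and 6, correlation 0.5 or 0.7. Subjects leave after month 1 at random, with probability logistic in the last observed change, or logistic in the unseen 6-month change (slope 0.4 or 0.8 per point). The true 6-month mean is 1.5.

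| Pattern of loss | Completers, 20% | Completers, 40% | Model using months 1, 3 and 6, 20% | Same model, 40% |
|---|---|---|---|---|
| Random | 1.49–1.51 | 1.47–1.48 | 1.49–1.52 | 1.48–1.50 |
| Poor responders leave after an observed score | 1.71–2.00 | 1.96–2.42 | 1.49–1.51 | 1.49–1.51 |
| Good responders leave after an observed score | 1.00–1.28 | 0.54–1.03 | 1.49–1.51 | 1.47–1.51 |
| Poor 6-month responders leave, score unseen | 1.96–2.19 | 2.40–2.80 | 1.73–2.03 | 1.97–2.55 |

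At 10% loss, observed-score patterns give completer means of 1.61–1.77 or 1.24–1.39. Reversing the unseen-score pattern gives completer means of 0.85–1.08 at 20%. The model therefore removes bias that the observed scores explain, and only reduces bias that they do not. Every simulated subject had a month 1 score, which favours the model.

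**Step 4: the plan's 2-point target.** A separate run with true mean 2.0, correlation 0.6 and loss depending on the month 3 change gave completer means of 2.22, 2.34 and 2.62 at 12%, 20% and 40% loss when non-responders leave, and 1.78, 1.66 and 1.32 when responders leave. An estimate using months 1 and 3 gave 1.97 to 2.00 throughout. With a true mean of 0 and non-responders leaving, favourable rejections by a two-sided 5% test (nominal 2.5%) were 5.6%, 9.2% and 16.3%.

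**Step 5: what a tipping-point table would show.** With 5 of 25 missing and an observed mean of 1.75, the all-treated mean is (20 × 1.75 + 5d) / 25. For d = −1, 0, +1 and +2 this is 1.20, 1.40, 1.60 and 1.80.

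**Step 6: ITT wording.** An enrolled but untreated subject has no 6-month post-injection score, so the t-test set is the same under either definition. Responder rates can differ: 15 responders of 25 treated is 60% (exact 95% CI 38.7–78.9%). If 5 enrolled-untreated subjects were counted as non-responders, 15 of 30 is 50% (31.3–68.7%). SAP 4.1.3.4 does not say how they would be counted.

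**The case against.** The strongest reply is that this is a small open-label post-market study that prespecified a simple test, pursues missing subjects, records why they leave and shows N at each visit. Loss may be small, and at 10% the shift is only 0.1 to 0.3 points. Because the test is against zero, a real effect's test result is less exposed than its estimate. All of that stands. It limits the problem but does not correct the mean.

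It is also fair that the t-test is in protocol 9.1. Replacing it in the SAP alone would put the two documents in conflict, and the fix below avoids this.

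Four stronger readings go too far:
- **Month 1 and 3 data are discarded.** They are tabulated with N, mean, SD and p-value, and subjects lost later still count in PP at those visits. They are unused only in the 6-month estimate.
- **The SAP excludes subjects without a 6-month score.** It never says so. The exclusion follows from the method and the lack of any other rule.
- **Readers are denied a range for the mean.** A t-based interval can be worked out from N, mean and SD. It is just not displayed.
- **Scores after a treatment-failure event distort the primary mean and nothing planned separates them.** Protocol 13.4 says "All subjects with protocol deviations will continue to be followed for improvement and safety" and "Analysis of study data will be done on both the ITT and PP populations", so such scores can enter the ITT mean. But enrolment required that "Subject must be willing to abstain from other treatments of the index joint for the duration of the study", so PP may leave these subjects out. The exploratory lists also include treatment failure, and SAP 4.1.4 compares subjects with and without non-drug therapy. An undefined major deviation is missing detail, not a demonstrated error.

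**Conclusion.** The point holds and should be fixed. As written, the 6-month ITT mean is in practice a completer mean, the 6-month PP mean is drawn from the same completers, and no planned analysis addresses loss related to response.

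Under the stated assumptions, the completer mean moves by about 0.1 to 0.3 points at 10% loss, 0.2 to 0.5 at 20% and 0.5 to 1.0 at 40% when loss follows an observed score. Loss that depends on the unseen 6-month score can move it further. Of the simulation inputs, the 25 subjects and SD 2.5 come from the plan; the rest are assumed.

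A reader might infer that the reported improvement will be inflated. The documents do not support that: they give neither a loss rate nor a reason to expect one direction, and random loss gives no bias. Confidence is high on the gap and low on its direction and size. The ITT mismatch is real but affects responder denominators, not the primary mean.

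**What to change.** 1. Keep the t-test as the primary test, so that protocol 9.1 and the SAP stay aligned. If it is to be replaced, amend both documents together.
2. In SAP 4.1.2.1, state how a missing 6-month score is handled. Add a prespecified repeated-measures estimate of the 6-month mean change with its 95% CI, using the 1-, 3- and 6-month NRS changes of all treated subjects (visit means, REML, unstructured covariance, Kenward-Roger degrees of freedom).
3. Add a tipping-point analysis that sets the mean change of missing subjects to, for example, −1, 0, +1 and +2 points, and report the range. Do not call zero change conservative, since its direction depends on who left. This step is needed because the model cannot fully correct for unseen scores or use subjects with no post-baseline score.
4. Show the 95% CI in the primary table.
5. Reconcile the ITT definition in SAP 4.5 with protocol 9.2.3 for MON 18-02. The hip and ankle protocols under the same SAP must be checked separately.

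**Cost.** SAP wording and some analysis code, with no new visits or data; the reported mean may be less favourable. In simulation the Kenward-Roger interval was on average no wider than the t-test interval (2.16–2.26 against 2.16–2.34 points at 20% loss; 2.42–2.64 against 2.45–2.79 at 40%). At 40% loss related to observed scores, its coverage was 89–94% against 66–90%. When 40% loss depended strongly on the unseen score, both fell short (46–64% against 31–33%), so the model should not be reported without the tipping-point analysis.
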